5.3 Lifestyle restrictions

5.3.1 Meals and dietary restrictions

- Study participants will complete a light meal approximately 30 minutes prior to each morning dose of CBD/PSL administration and will complete a standard meal approximately 30 minutes prior to the evening dose. On days when PK assessments will be taken, study participants will complete a similar meal between periods.
- Study participants will complete assessments on the morning of Day 1 and Day 15 of Treatment Period 1 (Part B) and at Screening under fasting conditions.
- Study participants should keep their usual diet (besides the restrictions for the study) necessary for the maintenance of good health; excessive food consumption should be avoided.

- Padsevonil will be administered orally with 8oz (240mL) of water. Between 1 hour predose and 2 hours postdose, the total intake of beverages should be limited to 100mL. Water will be available ad libitum except for between 1 hour before and 2 hours after dosing.
- Study participants should refrain from consumption of grapefruit, starfruit, and pawpaw (as beverage, fruit or supplements) from 3 days before the start of study treatment until after the final dose.

5.3.2 Caffeine, alcohol, and tobacco

- During each dosing session, participants will abstain from ingesting caffeine- or xanthine-containing products (eg, coffee, tea, cola drinks, and chocolate) for 48 hours before the start of dosing until after collection of the final PK and/or PD sample.
- During each dosing session, participants will abstain from alcohol for 24 hours before the start of dosing until after collection of the final PK and/or PD sample.
- Participants who use tobacco products will be instructed that use of nicotine-containing products (including nicotine patches) will not be permitted while they are in the clinical unit.

5.3.3 Activity

- Participants will abstain from strenuous exercise from 3 days prior to visit and during the study. Participants may participate in light recreational activities during the study (eg, watching television, reading, and playing table tennis).

5.4 Screen failures

Screen failures are defined as participants who consent to participate in the clinical study but are not subsequently entered in the study. A minimal set of screen failure information is required to ensure transparent reporting of screen failure participants to meet the Consolidated Standards of Reporting Trials (CONSORT) publishing requirements and to respond to queries from regulatory authorities. Minimal information includes demography, screen failure details, eligibility criteria, and any SAE.

5.4.1 Rescreening

Individuals who do not meet the criteria for participation in this study (screen failure) may be rescreened. Study participants may be rescreened under conditions such as the following:

- Study participant ingests grapefruit (as beverage, fruit, or supplements) within 72 hours before each administration of IMP.
- Study participant has a suspected false positive drug test.
- Study participant has a non-clinically significant vital signs measurement.
- If a study participant does not meet the exclusion criteria at Screening or on Day -1 due to an out-of-range laboratory result or a minor illness, he/she can be rescreened once at the discretion of the Investigator. Provided all inclusion criteria are met at the second Screening, the study participant can be included.

Study participants may be included if the repeat values for the laboratory screening criteria are within normal ranges and/or if repeat values show normalization of the out-of-range safety laboratory values, and/or after the study participant makes a complete recovery from the mild or moderate illness and if all other screening criteria are met.

Tests that result in ALT, AST, or ALP up to 25% above the exclusion limit may be repeated once for confirmation. This includes re-screening.

Rescreened participants will be assigned a new participant number.

6 STUDY TREATMENTS

Study treatment is defined as any investigational treatment(s), marketed product(s), placebo, or medical device(s) intended to be administered to a study participant according to the study protocol.

6.1 Treatments administered

A summary of the treatments administered is provided in [Table 6-1](#). Further Guidance or information are provided in the IMP Handling Manual.

This document cannot be used to support any marketing authorization application and any extensions or variations thereof.

REDACTED COPY

Table 6-1: Treatments administered

Study Treatment Name:	PSL	Placebo (for PSL)	Ethanol	Placebo (for ethanol) infusion	CBD
Dosage formulation:	Tablets	Matching PBO tablets	IV infusion	IV infusion	Solution/suspension
Unit dose strength(s)/Dosage level(s):	100mg, 100mg BID, 200mg BID	Matching PBO tablets	Alcohol 10% in Glucose 5%; Adjusted to maintain breath ethanol levels of 0.6g/L	Glucose 5%; 275mmol/L in bag of 500mL	Up to 10mg/kg BID ^a
Route of Administration	Oral	Oral	Infusion	Infusion	Oral
Dosing instructions:	Dosing instructions are provided in the “UP0071 IMP Handling Manual” (IP Instruction for Handling).				
Packaging and Labeling	PSL and matching PBO tablets are manufactured, packaged, and labeled according to Good Manufacturing Practice guidelines and applicable laws or regulations.		Ethanol and matching PBO are manufactured, packaged, and labeled according to Good Manufacturing Practice guidelines and applicable laws or regulations.		CBD is manufactured, packaged, and labeled according to Good Manufacturing Practice guidelines and applicable laws or regulations.
Manufacturer	UCB	UCB	LUMC	LUMC	EchoPharma

BID=twice per day; CBD=cannabidiol; h=hours; IP=investigational product; PBO=placebo; PK=pharmacokinetic. PSL=padsevonil; SmPC=Summary of Product Characteristics

^a Doses to be confirmed from CBD PK exposure in Part B, Treatment Period 1.

6.2 Preparation, handling, storage, and accountability requirements

The Investigator or designee must confirm appropriate temperature conditions have been maintained during transit for all study treatment received and any discrepancies are reported and resolved before use of the study treatment.

Only participants enrolled in the study may receive study treatment and only authorized site staff may supply or administer study treatment. All study treatments must be stored in a secure, environmentally controlled, and monitored (manual or automated) area in accordance with the labeled storage conditions with access limited to the Investigator and authorized site staff.

The Investigator, institution, or the head of the medical institution (where applicable) is responsible for study treatment accountability, reconciliation, and record maintenance (ie, receipt, reconciliation, and final disposition records).

In case an out-of-range temperature is noted, it must be immediately reported as per instructions contained in the IMP Handling Manual.

Further guidance and information for the final disposition of unused study treatment are provided in the "UP0071 IMP Handling Manual" (IP Instruction for Handling).

6.2.1 Drug accountability

A Drug Accountability form will be used to record study medication dispensing and return information on a by-participant basis and will serve as source documentation during the course of the study. Details of any study medication lost, damaged (due to breakage or wastage), not used, partially used, disposed of at the study site, or returned to the Sponsor or designee must also be recorded on the appropriate forms. All supplies and pharmacy documentation must be made available throughout the study for UCB (or designee) to review.

The Investigator (or designee) is responsible for retaining all used, unused, and partially used containers of study medication until returned or destroyed.

The Investigator may assign some of the Investigator's duties for drug accountability at the study site to an appropriate pharmacist/designee.

The Investigator must ensure that the study medication is used only in accordance with the protocol.

Periodically, and/or after completion of the clinical phase of the study, all used (including empty containers)/partially used, unused, damaged, and/or expired study medication must be reconciled and either destroyed at the site according to local laws, regulations, and UCB SOPs or returned to UCB (or designee). Investigational medicinal product intended for the study cannot be used for any other purpose than that described in this protocol.

6.3 Measures to minimize bias: randomization and blinding

A contract research organization (CRO; ie, ICON) randomization biostatistician will create the program to generate the randomization code and code break envelopes for each study part. The randomization biostatistician will be independent of the study. A dummy randomization schedule will be prepared by the randomization biostatistician (for Part A: cross-over 2x2 scheme with 4 treatment sequences; for Part B: cross-over 2x2 scheme with 2 treatment sequences) and

reviewed by the Clinical Study Biostatistician in order to ensure that the code meets the study requirements.

After finalization of the dummy code, the randomization program will be run with a different seed number to create the final randomization list; the final list will be generated in a secure environment and will be reviewed by a quality control randomization biostatistician, also independent of the study. These randomization lists (list of Part A and list of Part B) will be retained by ICON until the end of the study (ie, until after database lock). The treatment assignment will be random.

Copies of the randomization lists will be sent before the start of the study in a secure fashion directly from the contracted CRO to:

- Sponsor Patient Safety staff for SAE reporting (sealed envelope)
- Bioanalytical staff (to identify samples to be measured)
- Unblinded member of pharmacy involved in IMP preparation and dispensing or site quality/safety insurance
- Independent Biostatistician/Early Statistical Programmer

In addition, staff involved in the analysis of unblinded PK data, such as a representative from the UCB Clinical Pharmacology/Modeling and Simulation team and an unblinded monitor, will have access to the unblinded data during the study.

After eligibility of a participant has been confirmed, the study participants may be included and assigned to a subject number from 1 to 22 in Part A. Replacement study participants will be numbered +100 (eg, Study participant 5 will have Study participant 105 as replacement).

Similarly, for Part B, eligible study participant may be included and assigned a study participant number from 1001 to 1022. Replacement subjects will be numbered +100, e.g. Study participant 1005 will have Study participant 1105 as replacement.

In Part A and Part B, each study participant (screen failure and eligible) will receive a unique 5 digit UCB number assigned at Screening from a range of numbers supplied by UCB Clinical Data Operations, Technology, and Standards, which will serve as the UCB study participant identifier throughout the study.

Study participants that complete Part A of the study are not eligible to complete Part B; similarly, study participants that complete Part B are not eligible to complete Part A.

Once the Investigator determines that the study participant is eligible for the study, and before IMP administration, a central person in charge of issuing the randomization numbers will manually allocate a randomization number to the study participant (1 for each study part) and communicate the randomization assignment to the unblinded site pharmacist. Each specific randomization number will be linked to the treatment allocation on the randomization schedule, which will be dispensed by the unblinded site pharmacist. The randomization numbers will also be recorded in the eCRF.

6.3.1 Procedures for maintaining and breaking the treatment blind

6.3.1.1 Maintenance of treatment blind

All participant treatment details (treatments, Treatment Period, and treatment sequences) will be allocated and maintained through the use of randomization lists and emergency envelopes (or equivalent). The investigator and all study site personnel will be blinded to treatment assignments during the study.

6.3.1.1.1 Ethanol and matching placebo

To maintain blinding with respect to ethanol (ethanol 10% w/v solution in 5% glucose) and ethanol placebo (5% glucose), an individual who is not a member of the study team (has no responsibilities for study participant assessments) will obtain breath ethanol concentrations and adjust the infusion rate accordingly. For study participants randomized to ethanol, the infusion assistant will use actual breath ethanol concentration measurements to adjust the infusion rate according to an algorithm. For study participants randomized to placebo, the infusion assistant will use sham breath ethanol concentrations prepared prior to the study to make sham adjustments to the infusion rate.

6.3.1.1.2 PSL and matching placebo

A site pharmacist who is not a member of the study team (has no responsibilities for study participant assessments) will prepare PSL or PSL placebo treatment from bulk supplies in accordance with the randomization schedule supplied by the ICON unblinded Statistician.

6.3.1.2 Breaking the treatment blind in an emergency situation

An emergency envelope (or equivalent) containing the randomization code will be printed for each participant in a double-blind study and must not be broken, except for emergency situations. The CPM must be informed immediately when a code is broken, but should remain blinded to specific treatment information. Any unblinding of the study medication performed by the Investigator must be recorded in the source documents and on the Study Termination eCRF page.

6.4 Treatment compliance

Study participant compliance will be ensured by the administration of IMP by designated site personnel. Drug accountability must be recorded on the Drug Accountability form.

6.5 Concomitant medication(s)/treatment(s)

6.5.1 Permitted concomitant treatments (medications and therapies)

The following concomitant medications are permitted during the study:

- Paracetamol for the treatment of mild symptoms (eg, headache or other pain), given at most every 6h to 8h, not exceeding 2g/day, and with a total of no more than 5g over 7 days
- Inhaled corticosteroids for seasonal rhinitis
- Oral contraceptives not exceeding 30µg ethinyl estradiol or postmenopausal hormone replacement therapy or implants, patches, or IUDs/IUSs delivering progesterone (for female study participants)

6.5.2 Prohibited concomitant treatments (medications and therapies)

The following concomitant medications are prohibited during the study:

- With the exception of permitted concomitant treatments listed in Section 6.5.1, all prescription or nonprescription medicines are prohibited within 2 weeks or 5 half-lives whichever is longer of the respective drug prior to first administration of IMP and during the clinical part of the study unless required to treat an AE. This includes all OTC remedies, vitamins, and herbal and dietary supplements (including St. John's Wort).
 - Hepatic enzyme-inducing drugs (eg, glucocorticoids, phenobarbital, isoniazid, phenytoin, rifampicin etc.) should not be used within 2 months prior to dosing. In case of uncertainty, the Medical Monitor should be consulted.
- Drugs of unknown half-lives are prohibited within 2 weeks before administration of IMP and during the clinical part of the study, unless required to treat an AE.

If a study participant needs or takes any prohibited medication, the Investigator will (where possible) discuss with the Sponsor Study Physician and a decision will be made whether the study participant can continue in the study or must be withdrawn.

6.5.3 Rescue medication

Not applicable.

6.6 Dose modification

Dose modifications, in accordance with the Investigator and/or Sponsor, are permitted during the study for PSL and cannabidiol for an individual study participant. During the ethanol/placebo infusion, the infusion rate will be adjusted based on ethanol breath sampling.

6.7 Treatment after the end of the study

There are no plans for participant treatment after the end of the study.

7 DISCONTINUATION OF STUDY MEDICATION AND PARTICIPANT DISCONTINUATION/WITHDRAWAL

7.1 Discontinuation of study medication

Study medication will be stopped if the study participant develops a medical condition (or laboratory abnormality or ECG change) that, in the opinion of the Investigator, compromises the study participant's ability to participate or compromises the study participant's safety.

[figure not shown]
In all cases the study participant should be followed until the condition has resolved as agreed by the Investigator and the UCB Study Physician. If a participant discontinues study medication, no restart will be allowed.

7.1.1 Liver chemistry stopping criteria

Discontinuation of study treatment for abnormal liver function should be considered by the Investigator when a participant meets 1 of the conditions outlined in Figure 7-1 or if the Investigator believes that it is in best interest of the participant.

Study medication will be discontinued immediately and permanently for a participant if liver chemistry stopping criteria are met.

Figure 7-1: Liver chemistry stopping algorithm

ALT=alanine aminotransferase; INR=international normalized ratio; SAE=serious adverse event; ULN=upper limit of normal.

Specific assessments and follow-up actions for potential drug-induced liver injury are provided in Appendix 6 (Section 10.6).

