8.3.6 Adverse events of special interest

An AE of special interest is any AE that a regulatory authority has mandated be reported on an expedited basis, regardless of the seriousness, expectedness, or relatedness of the AE to the administration of a UCB product/compound. No AEs of special interest have been identified for PSL to date, with the exception of potential Hy's Law as described below.

Potential Hy's Law, defined as $\geq 3x$ ULN ALT or AST with coexisting $\geq 2x$ ULN total bilirubin in the absence of $\geq 2x$ ULN ALP, with no alternative explanation for the biochemical abnormality, must ALWAYS be reported to UCB as an AE of special interest (ie, without waiting for any additional etiologic investigations to have been concluded). Follow-up information should then be reported if an alternative etiology is identified during investigation and monitoring of the study participant.

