10.6 Appendix 6: Liver safety – suggested actions and follow-up assessments

Participants with potential drug-induced liver injury must be assessed to determine if study medication must be discontinued. In addition, all concomitant medications and herbal supplements that are not medically necessary should also be discontinued.

Investigators should attempt to obtain information on study participants in the case of study medication discontinuation to complete the final evaluation.

Study participants with potential drug-induced liver injury should not be withdrawn from the study until investigation and monitoring are complete. All results of these evaluations and observations, as well as the reason(s) for study medication discontinuation and/or participant withdrawal (if applicable), must be recorded in the source documents. The eCRF must document the primary reason for discontinuation of study medication.

A specific monitoring plan must be agreed between the UCB study physician and the Investigator for study participants who have ALT >5xULN. The monitoring plan should include any necessary follow-up assessments (until resolution of the abnormal lab values).

Phase 1 liver chemistry stopping criteria are designed to assure participant safety and to evaluate liver event etiology (Table 10-2).

Table 10-2: Phase I liver chemistry stopping criteria and follow-up assessments

Liver Chemistry Stopping Criteria – Liver Stopping Event	
ALT-absolute	ALT ≥ 3xULN If ALT ≥ 3xULN AND bilirubin ≥ 2xULN (>35% direct bilirubin) OR international normalized ratio (INR) > 1.5, report as a serious adverse event (SAE). ^{a,b} See additional actions and follow-up assessments listed below
Suggested Actions and Follow up Assessments	
Actions	Follow Up Assessments

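### Section 7.1.1 makes the liver stop both discretionary and mandatory, and the visible criteria are ALT-only, so a potential Hy's Law case met through AST alone has no automatic stop and no timed retest

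*Protocol*

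**What the plan says.** Protocol 7.1.1 has two operative sentences. The first says that discontinuation for abnormal liver function "should be considered by the Investigator when a participant meets 1 of the conditions outlined in Figure 7-1", or when the Investigator thinks it is in the participant's best interest. The second reads: "Study medication will be discontinued immediately and permanently for a participant if liver chemistry stopping criteria are met". The figure is titled as the liver chemistry stopping algorithm. Its body is not in the text available, but its abbreviation list reads "ALT=alanine aminotransferase; INR=international normalized ratio; SAE=serious adverse event; ULN=upper limit of normal".

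Appendix 6 (Section 10.6) is headed as "suggested actions and follow-up assessments". Its Table 10-2 carries the stopping criteria in its title and has one stopping event, ALT at or above 3xULN. The escalation to SAE reporting begins "If ALT ≥ 3xULN AND bilirubin ≥ 2xULN (>35% direct bilirubin", with raised INR as the alternative to bilirubin. Both monitoring schedules start from ALT at or above 3xULN: repeat within 24 hours then twice weekly, or repeat within 24 to 72 hours then weekly. Appendix 6 also says: "A specific monitoring plan must be agreed between the UCB study physician and the Investigator for study participants who have ALT >5xULN".

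Section 8.3.6 defines potential Hy's Law as ALT or AST at or above 3xULN with total bilirubin at or above 2xULN, ALP below 2xULN and no alternative explanation. Such a case "must ALWAYS be reported to UCB as an AE of special interest". SAP 11.3 also counts either enzyme in its listing of potential drug-induced liver injury (PDILI).

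**The concern.** The first problem is the force of the rule. If the figure's conditions are the stopping criteria, the same ALT result is a matter for consideration in one sentence and an unconditional stop in the next. A site relying on the first could continue dosing, and a monitor relying on the second could record that as a breach. The choice matters because Sections 7.1 and 7.1.2 allow no restart: a stop cannot be undone, whereas a decision to continue can be revisited.

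The second problem is reach. The protocol treats AST as equal to ALT when it defines its most serious liver signal, and again at entry (exclusion criterion 14), but not in the visible stopping event or the timed follow-up. The participants are healthy volunteers who receive no medical benefit (Section 2). For them, two cases with the same bilirubin get different automatic protection depending on which transaminase is raised.

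**Working it through.** The main check is a comparison of texts. Only the cost of the fix involves arithmetic.

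**Step 1. Force of the stop.** Take ALT 3.2xULN with normal bilirubin. The Table 10-2 stopping event is met, so the mandatory sentence of 7.1.1 applies. If Figure 7-1 carries the same threshold, as its title suggests, the discretionary sentence applies too. No text ranks the two.

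**Step 2. Reach to AST.** Compare two cases. Case A has AST 4xULN, ALT 2.5xULN, total bilirubin 2.2xULN, ALP 1.2xULN and no alternative cause. Case A' is the same with ALT 3.2xULN.

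| Provision | Case A (AST-led) | Case A' (ALT also raised) |
|---|---|---|
| Potential Hy's Law, reported as AESI (8.3.6) | Yes | Yes |
| Visible stopping event (Table 10-2) | No | Yes |
| Suggested 24-hour repeat, then twice weekly (Table 10-2) | No | Yes |
| SAE wording | Usually serious, as an example of an important medical event (10.3.2) | Must be an SAE (Appendix 2 footnote 2; Table 10-2 footnote b), given the direct-bilirubin or INR qualifier |
| Stop if the Investigator judges safety compromised (7.1; 7.2 item 1; best-interest clause of 7.1.1) | Yes, by judgement | Yes |
| PDILI assessment (Appendix 6) | Yes | Yes |
| Immediate Sponsor discussion (Section 8) | Yes | Yes |
| Repeat of clinically significant values (8.2.4) | Yes, no interval given | Yes |

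The agreed monitoring plan shows the same asymmetry. AST 6xULN with ALT 2.5xULN does not require one; ALT 6xULN does.

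**Step 3. Scheduled draws if no retest time is set.** In Part B, Table 1-7 puts chemistry on Days -1, 7 and 16 of Period 3, which is ambulatory: 16 - 7 = 9 days between the last two draws, during and after cannabidiol up-titration. Table 1-8 has chemistry only on Day 7 of Periods 4 and 5. SAP Table 3-3 maps these to phase days 23 and 34: 34 - 23 = 11 days, longer if the interval between those periods is extended. Section 8.2.4 asks for repeats in between but sets no time.

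**Step 4. Cost of one extra, unreplaced discontinuation in Part A.** Inputs from Protocol 9.10: difference 3.96, SD of difference 6.0, two-sided paired t-test, alpha 0.05, n = 22, stated power 80%. The noncentrality is (3.96/6.0) x sqrt(n), with power from the noncentral t distribution on n - 1 degrees of freedom.

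- n = 22: noncentrality 0.66 x 4.690 = 3.096, critical t 2.080, power 83.9%. The plan's 80% is met with some margin.
- n = 21: noncentrality 0.66 x 4.583 = 3.024, critical t 2.086, power 82.0%.
- n = 20: noncentrality 0.66 x 4.472 = 2.952, critical t 2.093, power 79.95%.

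One loss is 1/22 = 4.5% of Part A and keeps power above 80%. Two losses bring it marginally below.

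**The case against.** The strongest reply is that the mandatory sentence has its own clear referent. Table 10-2 is titled as the stopping criteria and names a stopping event, so the unconditional sentence controls there and discretion covers what falls outside it. That is the sensible reading, but the text does not state it, and the discretionary sentence points to a figure that is itself called the stopping algorithm.

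A second reply is that Figure 7-1 cannot be seen. It may have several branches and may say which of them require a stop. Its legend is weak evidence that AST is absent, since legends elsewhere in the protocol are incomplete (Table 1-1 uses SEM and IMP without defining them). This stands as a limit: the finding concerns the visible criteria, and any edit to the figure is conditional on what it contains.

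A third reply is that AST-led cases are already covered by judgement. That is true. A reader might infer that such a case could continue on drug with nothing done. The documents do not support this: Section 7.1 requires a stop when the Investigator thinks safety is compromised, 7.2 item 1 and the best-interest clause of 7.1.1 reach the same case, and assessment, Sponsor discussion and repeat testing all apply. What is missing is an automatic threshold and a retest time.

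A reader might also take the Appendix 6 opening, "Participants with potential drug-induced liver injury must be assessed to determine if study medication must be discontinued", as a third and conflicting force on the same criterion. It is not one. It addresses potential drug-induced liver injury generally, a broader group (the SAP listing includes raised ALP or bilirubin alone), and assessing that group is compatible with an automatic stop at ALT 3xULN.

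Finally, ALT-only stopping may be deliberate, and entry criteria and short padsevonil exposure (10 days in Part A, 21 in Part B) make liver events unlikely. The documents give no reason for leaving AST out. The low expected frequency limits the weight of the point without removing it.

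**Conclusion.** The concern holds in a limited form. Section 7.1.1 attaches two forces to what reads as one set of liver criteria. Separately, a potential Hy's Law case reached through AST alone has no automatic, threshold-based stop and no timed retest in the visible text. The first is a drafting fault; the second is a design gap that is cheap to close.

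The size is qualitative: the frequency of AST-only cases cannot be estimated from the documents, and no endpoint or estimate is affected. The conclusion assumes that Figure 7-1 matches Table 10-2. If the figure has an AST branch or ranks the two sentences, the corresponding part falls away.

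A reader might infer from the Part A figures that losing a participant also leaves the Part B precision target intact. That should not be assumed. Protocol 9.10 asks for a half-width of 0.3 with 90% conditional probability. On a log-scale model with CV 45% and correlation 0.5, the SD of the difference is sqrt(ln(1 + 0.45^2)) = 0.429. The unconditional probability of a half-width of at most 0.3 at a ratio of 1.5 is then 0.65 at n = 22 and 0.58 at n = 21. Part B precision is a separate matter and does not bear on the liver wording.

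**What to change.** In 7.1.1, state that discontinuation is immediate and permanent when a stopping criterion in Table 10-2 or Figure 7-1 is met. Limit the discretionary sentence to other liver abnormalities and to the Investigator's best-interest judgement.

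In Table 10-2, and in Figure 7-1 if it is also ALT-only, add any case meeting the full 8.3.6 definition (ALT or AST) as a liver stopping event, with the 24-hour repeat and twice-weekly schedule. Extend the agreed monitoring plan above 5xULN to either enzyme. In Appendix 2 footnote 2 and Table 10-2 footnote b, change the possible Hy's Law SAE wording to ALT or AST, keeping the direct-bilirubin and INR qualifiers.

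No scheduled test is added: AST, ALT, ALP and bilirubin are already in the Appendix 2 panel. Using the full 8.3.6 definition, rather than isolated AST, means that a bilirubin rise explained by Gilbert's syndrome, which is allowed at entry, does not by itself force a stop. It also leaves some judgement in the trigger, because whether an alternative explanation exists must be decided at the time.

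The cost is a rare extra discontinuation, possibly without the taper that Sections 7.1.3 and 7.2 favour. The participant can be replaced at the discretion of the Investigator and Sponsor; the Part A figures above show the effect if not.
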